## 5. STATISTICAL ANALYSES

That standard data derivation rules and stat methods are described in Section 10.1 while the study specific data derivation rules and statistical methods are described in Section 9.

### 5.1. Demography

#### 5.1.1. Analysis of demographics/baseline characteristics planned in the protocol

The analysis of demographic characteristics by group will be performed on the ES and on the PPS.

Demographic characteristics (age at vaccination in years, sex, race and ethnicity) will be summarized by group using descriptive statistics:

- Frequency tables will be generated for categorical variables such as race.
- Mean, median, standard deviation and range will be provided for continuous data such as age.

The distribution of subjects will be tabulated as a whole and per group and for each age category (60-69 years and 70-80 years).

Withdrawal status will be summarized by group using descriptive statistics:

- The number of subjects enrolled into the study as well as the number of subjects excluded from Per Protocol (PP) analyses will be tabulated.
- The numbers of withdrawn subjects will be tabulated according to the reason for withdrawal.

## **5.1.2. Additional considerations**

Vital signs (heart rate, respiratory rate, systolic/diastolic blood pressure, pulse oximetry) reported at visit 1 will be summarized by study group using descriptive statistics.

## **5.2. Exposure**

### **5.2.1. Analysis of exposure planned in the protocol**

NA

### **5.2.2. Additional considerations**

The number of doses of study vaccines administered will be tabulated by group and by vaccine.

## **5.3. Immunogenicity**

The primary analysis will be based on the Per Protocol set for analysis of immunogenicity. If in any study group and at any timepoint, the percentage of vaccinated subjects with serological results excluded from the Per Protocol set for analysis of immunogenicity is 10% or more, a second analysis based on the Exposed set will be performed to complement the Per Protocol analysis.

### **5.3.1. Analysis of immunogenicity planned in the protocol**

#### **5.3.1.1. Humoral immune response**

For each group, at each time point that blood samples are collected for humoral immune response and for each assay (unless otherwise specified):

- Percentage of subjects above pre-defined threshold and their exact 95% CI will be tabulated.
- Geometric mean concentrations (GMCs)/ geometric mean titers (GMTs) and their 95% CI will be tabulated and represented graphically.
- Antibody titer/concentration will be displayed using reverse cumulative curves.
- The distributions of antibody titers/concentrations will be tabulated.
- Geometric mean of ratios of antibody titer/concentrations at each post-vaccination time point over pre-vaccination (Day 1) will be tabulated with 95% CI.
- Individual post-vaccination results (at Days 31, 61 and 91) versus pre-vaccination results (Day 1) will be plotted using scatter plots. Results of the placebo group will be used as a reference.
- Distribution of the fold increase of the antibody titers/concentrations (post- over pre-vaccination titers) will be tabulated.

- The ratio of fold increase (post over pre-vaccination) of RSVPreF3 ELISA antibody concentrations over the fold increase (post over pre-vaccination) of RSV-A and RSVB neutralizing antibody titers will be computed and tabulated using descriptive statistics.
- The kinetics of GMT/GMCs will be plotted as a function of time for subjects with results available at all time points.

The immunogenicity analysis might also be performed by age category (60-69 years and 70-80 years).

## **5.4. Analysis of safety and reactogenicity**

The primary analysis will be performed on the Exposed Set.

### **5.4.1. Analysis of safety and reactogenicity planned in the protocol**

- The percentage of subjects with at least one local AE (solicited and unsolicited), with at least one general AE (solicited and unsolicited) and with any AE during the 7-day or 30-day follow-up period will be tabulated with exact 95% confidence interval (CI) after each dose and overall. The same computations will be done for Grade 3 AEs, for any AEs considered related to vaccination, for Grade 3 AEs considered related to vaccination and for Grade 3 non-serious AEs.
- The percentage of subjects with any AE (solicited and unsolicited) resulting in a medically attended visit during the 30-day follow-up period will also be tabulated after each dose and overall.
- The percentage of subjects reporting each individual solicited local AE (any grade and Grade 3) and solicited general AE (any grade, Grade 3, any related and Grade 3 related) during the 7-day follow-up period (i.e., on the day of vaccination and 6 subsequent days) will be tabulated for each group after each dose and overall.
- For fever, the number and percentage of subjects reporting fever by half degree (°C) cumulative increments during the 7-day follow-up period (i.e., on the day of vaccination and 6 subsequent days) will be tabulated for each group after each dose and overall. Similar tabulations will be performed for any fever with a causal relationship to vaccination and for Grade 3 ( $> 39.0^{\circ}\text{C}$ ) causally related fever. In addition, the prevalence of any and Grade 3 fever will be presented graphically over time after each vaccination.
- For each group and for each hematology and biochemistry parameter:
  - i. The percentage of subjects having hematology and biochemistry results below or above the laboratory normal ranges will be tabulated by time point.
  - ii. The summary of grading post-vaccination will be tabulated versus baseline. Grades will be based on the FDA Guidance for Industry “Toxicity Grading Scale for Healthy Adults and Adolescent Volunteers Enrolled in Preventive Vaccine Clinical Trials”, see Protocol Section 12.7 The laboratory parameters not included on FDA Toxicity Grading Scale will not be graded.

- The percentage of subjects with any unsolicited AEs during the 30-day follow-up period (i.e., on the day of vaccination and 29 subsequent days) with its exact 95% CI will be tabulated by group and by Medical Dictionary for Regulatory Activities (MedDRA) preferred term. Similar tabulation will be done for Grade 3 unsolicited AEs, for any causally related unsolicited AEs, for Grade 3 causally related unsolicited AEs and for unsolicited AEs resulting in a medically attended visit. The verbatim reports of unsolicited AEs will be reviewed by a qualified person and the signs and symptoms will be coded according to the MedDRA Dictionary for Adverse Reaction Terminology. Every verbatim term will be matched with the appropriate Preferred Term.
- The percentage of subjects with at least one report of SAE classified by the MedDRA Preferred Terms and reported from Dose 1 up to 30 days after the second vaccine dose (Day 91) will be tabulated with exact 95% CI.
- The percentage of subjects with at least one pIMD classified by the MedDRA Preferred Terms and reported from Dose 1 up to 30 days after the second vaccine dose (Day 91) will be tabulated with exact 95% CI.
- The percentage of subjects with at least one report of SAE classified by the MedDRA Preferred Terms and reported during the entire study period will be tabulated with exact 95% CI. SAEs will also be described in detail.
- The percentage of subjects with at least one pIMD classified by the MedDRA Preferred Terms and reported during the entire study period will be tabulated with exact 95% CI. pIMDs will also be described in detail.

The analysis of safety might also be performed by age category (60-69 years and 70-80 years).

#### **5.4.2. Additional considerations**

- Compliance in completing solicited adverse events information will be tabulated after each dose and overall.
- The percentage of subjects using concomitant medication (any medication, any antipyretic and any antipyretic taken prophylactically, respectively) during the 7-day follow-up period (i.e., on the day of vaccination and 6 subsequent days) and during the 30-day follow-up period (i.e., on the day of vaccination and 29 subsequent days) will be summarized by group after each vaccine dose and overall.
- The percentage of subjects reporting each individual solicited local AE (any grade and Grade 3) and solicited general AE (any grade, Grade 3, any related and Grade 3 related) during the 4-day follow-up period (i.e., on the day of vaccination and 3 subsequent days) will be tabulated for each group after each dose and overall.
- The percentage of subjects with at least one local solicited AE, with at least one general solicited AE and with any solicited AE during the 7-day and 4-day follow-up period will be tabulated with exact 95% confidence interval (CI) after each dose and overall. The same computations will be done for Grade 3 AEs, for any AEs considered related to vaccination, and for Grade 3 AEs considered related to vaccination.

- The number of days with solicited symptoms reported during the 7-day follow-up period will be tabulated for each solicited adverse event, after each dose using descriptive statistics (mean, min, Q1, median, Q3, maximum). The same tabulation will be done for Grade 3 symptoms, and also during the whole post-vaccination period (to include the total number of days for symptoms ongoing beyond the follow-up period).
- The incidence of each solicited symptom (any grade and grade 3) will also be represented graphically per group and per dose.

#### 5.4.2.1. **Solicited Adverse Events**

Solicited adverse events will be reported daily during the 7-day follow up period after each vaccination by the subject in the eDiaries. Missing or non-evaluatable measurements will not be replaced. The data will be made available for site follow-up on the eDiary web-portal.

In order to summarize the data, the maximum intensity of local injection site redness/swelling (in mm) and fever (in °C) will be categorized as follows

Grading	Redness/swelling	Fever
0:	≤ 20 mm	< 38.0°C
1:	> 20 - ≤ 50 mm	≥ 38.0°C - ≤ 38.5°C
2:	> 50 - ≤ 100 mm	> 38.5°C - ≤ 39.0°C
3:	> 100 mm	> 39.0°C

Fever is defined as temperature  $\geq 38.0^{\circ}\text{C}$  (regardless of the location of measurement). The preferred location for measuring temperature in this study will be the oral cavity. Body temperature will also be summarized by  $0.5^{\circ}\text{C}$  increments as follows:  $\geq 38.0, > 38.5, > 39.0, > 39.5, > 40.0^{\circ}\text{C}$ .

Each subject's data will be summarized according to the maximal severity observed during the follow-up period for each adverse event and each dose, followed by a summary across subjects and across doses.

The intensity should be assigned to 1 of the following categories:

1 (mild)	= An AE which is easily tolerated by the subject, causing minimal discomfort and not interfering with everyday activities.
2 (moderate)	= An AE which is sufficiently discomforting to interfere with normal everyday activities.
3 (severe)	= An AE which prevents normal, everyday activities. In adults, such an AE would, for example, prevent attendance at work and would necessitate the administration of corrective therapy.

#### 5.4.2.2. **Unsolicited Adverse Events**

When an unsolicited adverse event occurs more than once for a subject, the maximal severity and strongest relationship to the vaccine group will be counted. The selection of unsolicited AEs reported during the follow-up period will be done using the day of onset.

The analysis of unsolicited adverse events includes the following categories:

- Any unsolicited adverse event
- Possibly related unsolicited adverse events
- Grade 3 unsolicited adverse events
- Grade 3 possibly related unsolicited adverse events
- Serious adverse events (SAEs)
- Possibly related SAEs
- Potential immune-mediated disease (pIMD)
- Medically attended adverse events

SAEs and pIMDs reported during the entire study period will be tabulated.

In addition, the following time periods will be considered to report SAEs/pIMDs at the first and end of study analyses (E1\_02 and E1\_01, see section 7.1):

- from Dose 1 up to 30 days post-dose 2 (or up to 90 days post-dose 1 for subjects who did not receive the second dose)

\* months will be converted in days in order to select the events for the output tables.

- Listing of AEs/SAEs leading premature withdrawal from study or to interruption of vaccination will be described in detail.

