**Table 26      Intensity scales for solicited symptoms in adults**

Adults		
Adverse Event	Intensity grade	Parameter
Pain at injection site	0	None
	1	Mild: Any pain neither interfering with nor preventing normal every day activities.
	2	Moderate: Painful when limb is moved and interferes with every day activities.
	3	Severe: Significant pain at rest. Prevents normal every day activities.
Redness at injection site		Record greatest surface diameter in mm
Swelling at injection site		Record greatest surface diameter in mm
Fever*		Record temperature in °C (with 1 decimal)
Headache	0	Normal
	1	Mild: Headache that is easily tolerated
	2	Moderate: Headache that interferes with normal activity
	3	Severe: Headache that prevents normal activity
Fatigue	0	Normal
	1	Mild: Fatigue that is easily tolerated
	2	Moderate: Fatigue that interferes with normal activity
	3	Severe: Fatigue that prevents normal activity
Gastrointestinal symptoms (nausea, vomiting, diarrhea and/or abdominal pain)	0	Normal
	1	Mild: Gastrointestinal symptoms that are easily tolerated
	2	Moderate: Gastrointestinal symptoms that interfere with normal activity
	3	Severe: Gastrointestinal symptoms that prevent normal activity
Arthralgia	0	Normal
	1	Mild: Arthralgia that is easily tolerated
	2	Moderate: Arthralgia that interferes with normal activity
	3	Severe: Arthralgia that prevents normal activity
Myalgia	0	Normal
	1	Mild: Myalgia that is easily tolerated
	2	Moderate: Myalgia that interferes with normal activity
	3	Severe: Myalgia that prevents normal activity
Shivering	0	Normal
	1	Mild: Shivering that is easily tolerated
	2	Moderate: Shivering that interferes with normal activity
	3	Severe: Shivering that prevents normal activity

\*Fever to be reported as AE is defined as temperature  $\geq 38.0^{\circ}\text{C}$ . The preferred location for measuring temperature in this study will be the oral cavity.

The maximum intensity of local injection site redness/swelling and fever will be scored at GSK as follows:

	Redness/swelling	Fever
0:	≤ 20 mm	< 38.0°C
1:	> 20 - ≤ 50 mm	≥ 38.0°C - ≤ 38.5°C
2:	> 50 - ≤ 100 mm	> 38.5°C - ≤ 39.0°C
3:	> 100 mm	> 39.0°C

The investigator will assess the maximum intensity that occurred over the duration of the event for all unsolicited AEs (including SAEs) recorded during the study. The assessment will be based on the investigator's clinical judgement.

The intensity should be assigned to 1 of the following categories:

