#### *Assessment of causality*

The investigator is obligated to assess the relationship between study vaccine and the occurrence of each AE/SAE using clinical judgement.

Alternative plausible causes, such as natural history of the underlying diseases, concomitant therapy, other risk factors, and the temporal relationship of the event to the study vaccine will be considered and investigated. The investigator will also consult the IB to determine his/her assessment.

There may be situations when an SAE has occurred and the investigator has minimal information to include in the initial report to GSK. However, it is very important that the investigator always makes an assessment of causality for every event prior to submission of the Expedited Adverse Events Report to GSK. The investigator may change his/her opinion of causality in light of follow-up information and update the SAE information accordingly. The causality assessment is one of the criteria used when determining regulatory reporting requirements.

All solicited local (injection site) reactions will be considered causally related to vaccination. Causality of all other AEs should be assessed by the investigator using the following question:

*Is there a reasonable possibility that the AE may have been caused by the study vaccine?*

YES : There is a reasonable possibility that the study vaccine contributed to the AE.

NO : There is no reasonable possibility that the AE is causally related to the administration of the study vaccine. There are other, more likely causes and administration of the study vaccine is not suspected to have contributed to the AE.

If an event meets the criteria to be determined as 'serious' (see Section 12.5.2), additional examinations/tests will be performed by the investigator in order to determine ALL possible contributing factors for each SAE.

Possible contributing factors include:

- Medical history.
- Other medication.
- Protocol required procedure.
- Other procedure not required by the protocol.
- Lack of efficacy of the vaccine, if applicable.
- Erroneous administration.
- Other cause (specify).

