**10.1.3.6. Counting rules for combining solicited and unsolicited adverse events**

For output combining solicited and unsolicited adverse events, all serious adverse events will be considered general events since the administration site flag is not included in the expedited adverse event CRF pages.

Multiple events with the same preferred term which start on the same day are counted as only one occurrence.

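### The SAP's rule for repeat unsolicited AEs does not tie severity and causality to the same occurrence, so the joint Grade 3 related count is ambiguous and could include an event that no subject had

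*SAP*

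**What the plan says.** SAP 5.4.2.2 contains the only counting rule for unsolicited AEs that recur. Its trigger is "When an unsolicited adverse event occurs more than once for a subject", and its instruction is that "the maximal severity and strongest relationship to the vaccine group will be counted". The list of analysis categories that follows includes a joint one: "Grade 3 possibly related unsolicited adverse events".

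That joint category is used in SAP 5.4.1, which repeats Protocol 10.3.2. There the percentage of subjects is tabulated by group and preferred term with exact 95% confidence intervals, and further tabulations of the same kind are planned "for Grade 3 causally related unsolicited AEs and for unsolicited AEs resulting in a medically attended visit".

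Both attributes are recorded event by event (Protocol 12.5.7.2.2). For intensity, "The investigator will assess the maximum intensity that occurred over the duration of the event for all unsolicited AEs". Causality is a yes/no answer for each AE, where yes means "There is a reasonable possibility that the study vaccine contributed to the AE". The strongest relationship among repeats therefore means that at least one of them was judged related.

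**The concern.** The rule takes two maxima over a subject's occurrences and does not require one occurrence to carry both. That is harmless in a table showing severity alone or relationship alone. It causes trouble only where the two are combined.

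If one episode is Grade 3 and unrelated and another is Grade 1 and related, no episode has both the maximal severity and the strongest relationship. Taken literally, the rule can only be met by borrowing one attribute from each. The subject then appears as Grade 3 related, an assessment the investigator never made.

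The trial has about 20 subjects per group and is purely descriptive, so readers will look at individual cells. Two programmers could each follow the SAP faithfully and produce different counts.

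**Working it through.** **1. Does any other text settle it?**

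| Text | What it does | Does it link severity to relationship? |
|---|---|---|
| SAP 5.4.2.2 | Takes maxima over repeat unsolicited AEs | No |
| SAP 5.4.1 | Tabulates subjects, "for Grade 3 causally related unsolicited AEs" among the categories | Possibly, if read as selecting single events; not stated |
| SAP 5.4.2.1 | Maximum severity for solicited AEs, per event and per dose | No; it concerns solicited AEs only |
| SAP 10.1.3.6 | "Multiple events with the same preferred term which start on the same day are counted as only one occurrence", for output combining solicited and unsolicited AEs | No |
| SAP 9 | Partial dates | No |

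The solicited rule works dose by dose. The unsolicited rule has no such limit, so an episode after Dose 1 could be pooled with one after Dose 2.

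**2. Worked case.** One subject has two occurrences of one preferred term: A is Grade 3 and not related, B is Grade 1 and related.

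- Separate maxima: severity = max(3, 1) = 3; relationship = max(no, yes) = yes. Counted as Grade 3 related.
- Same occurrence required: A is Grade 3 but not related; B is related but not Grade 3. Not counted.
- Grade 3 alone, and related alone: counted once in each under both readings. These cells do not change.

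**3. The plan's own figures.** Protocol 10.1.1 justifies 20 per group by the chance of seeing at least one AE, 1 − (1 − p)^20:

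- p = 7.8%: 80.3% (stated 80%)
- p = 10.9%: 90.1% (stated 90%)

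Both reproduce. So do the Clopper-Pearson limits in Protocol Table 19 for the rows needed here:

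| Count | Percentage | 95% limits |
|---|---|---|
| 0/20 | 0% | 0.00 to 16.84 |
| 1/20 | 5% | 0.13 to 24.87 |
| 2/20 | 10% | 1.23 to 31.70 |

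**4. Size if a case occurs.** One subject is 1/20 = 5 percentage points. If it is the only count in the cell, 0% becomes 5% and the upper limit rises by 24.87 − 16.84 = 8.03 points.

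**5. How often?** The documents give no rate of repeat events. As an illustration only, assume two independent occurrences, each Grade 3 with probability g and related with probability r. A spurious count needs one occurrence to be Grade 3 and unrelated and the other to be lower grade and related:

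P = 2 × g(1 − r) × (1 − g)r

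- g = 5%, r = 10%: 2 × 0.05 × 0.90 × 0.95 × 0.10 = 0.9%
- g = 20%, r = 50%: 2 × 0.20 × 0.50 × 0.80 × 0.50 = 8.0%

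These are probabilities per subject who has a repeat event. If, again by assumption, 4 of 20 subjects in a group had one, the expected number of spurious subjects would be about 4 × 0.0086 = 0.03 to 4 × 0.08 = 0.32.

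**The case against.** The strongest reply is that the SAP already means event-level counting. SAP 5.4.1 attaches Grade 3 and causally related to the same AE, and words the combined solicited and unsolicited tabulation in the same way. That section restates what the protocol planned, whereas 5.4.2.2 sits under additional considerations. SAP section 8 reports no changes from the planned analyses, and a composite that no subject experienced would be a change. On this view 5.4.2.2 only collapses repeats: maximal severity for severity tables, strongest relationship for relationship tables. The table layouts, which might settle the matter, are in a separate document (SAP 10.2).

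Much of this stands. It shows that the event-level reading is available, and perhaps the more natural one, so a reader who infers that the written rule necessarily creates false Grade 3 related events goes too far. It does not remove the ambiguity: 5.4.2.2 is the only repeat-event rule, it stands directly above the affected category, and nothing says that 5.4.1 prevails.

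Other points on that side also hold:

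- Grade 3 related unsolicited AEs are not an endpoint. The tabulation is one of several analyses supporting the primary safety endpoint.
- Any error overcounts harm, which is the cautious direction.
- Individual listings at the end of study would let an odd cell be checked. The Day 91 analysis, treated as final for its endpoints, gives the study team none.

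**Conclusion.** The ambiguity is real and narrow. Read literally, the rule would place a subject with discordant repeats in the Grade 3 related category without any such event having occurred, and no other text in the SAP excludes that. The effect is confined to the joint Grade 3 related cells. One case adds 5 percentage points in a group of 20. The frequency cannot be estimated from the documents and is probably low, because it needs the same AE to recur in one subject with discordant grade and causality and no single occurrence that is both Grade 3 and related. I have taken the same AE to mean the same preferred term, which is how the tables are built.

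A reader might infer two further things that the documents do not support:

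- **Distortion of the comparison with placebo.** The artefact needs at least one related episode, so it would tend to fall on the arm with more of them. That this is the vaccine arm is plausible, but nothing in the documents shows it, and no between-group test is planned.
- **An effect on holding rule 2d.** Nothing links this counting rule to the safety committee's assessment of that rule.

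Priority is low and confidence moderate.

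**What to change.** Add to SAP 5.4.2.2:

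> Joint categories are derived at event level. A subject is counted as having a Grade 3 related unsolicited AE only if at least one single occurrence is both Grade 3 and related. Maximal severity and strongest relationship across occurrences are used only in tables that show that one attribute.

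State also whether repeats are collapsed within each dose or across both doses, and align the programming of the SAP 5.4.1 tabulations with this text.

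The cost is two or three sentences. No new data are needed, since grade and causality are already collected for each event, and the separate Grade 3 and related counts do not change.
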